5.0 Study Procedures

5.1 Study Design

This is an observational multi-method cross-sectional study with transgender Veterans that will identify barriers and facilitators associated with GAT receipt among trans Vets who desire GATs. We will also identify patient-centered strategies to address barriers and enhance facilitators to improve GAT access. The proposed study will use a mixed-methods design, with three aims. We begin with obtaining national VA data to provide a foundational lay of the land on the GATs received by trans Vets in VA and/or CC (database Aim 1). Next, using a national cross-sectional survey, we will identify barriers and facilitators associated with receipt of desired GATs in VA and CC (survey Aim 2). Finally, by interviewing trans Vets and LGBTQ+ VCCs, we

will understand experiences and perspectives on GAT access in VA and CC, and how to improve this access in VA and CC (qualitative Aim 3).

Database Aim 1: We will expand our VA cohort of 9,608 trans Vets (IIR 17-238) from 2006-18 to the data available at the time of funding. We will add CC data to determine the types of GATs received by trans Vets in VA and/or CC. Aim 1 of the study will consist of all Veterans with documentation of a gender dysphoria (GD) diagnosis code in the VA or in CC from 1999 to the current year for which VA and CC data is available.

Survey Aim 2: We will survey a national sample of up to 1,500 trans Vets with a documentation of a gender dysphoria (GD) diagnoses identified from Aim 1 in the VA or CC in the past 2 years at the time of funding. Among trans Vets who desire GATs, we will determine barriers, and facilitators associated with desired GAT receipt. Among trans Vets who did not desire GATs, we will determine reasons for not wanting GATs. Veterans will be invited by postal mail, email, and phone to participate in a single survey. Similar to our pilot testing recruitment, we will also advertise the survey on VA's LGBTQ+ Health Office website and we will work on recruitment with LGBTQ+ Veteran Care Coordinators (VCCs). Veterans will be encouraged to complete the survey online but will have the option to complete the survey by phone or mail if desired. Data from the survey will be linked to CDW data (available through VINCI) via a study ID, and the crosswalk file will be stored in a separate secure file and will only be accessible to study team members.

Qualitative Aim 3: From Aim 2 participants, we will recruit a purposive sample of approximately 70 trans Vets. We will also recruit a national sample of approximately 20 LGBTQ+ Veteran Care Coordinators (VCCs). We will seek to understand experiences and perspectives on GAT access in VA and CC, how barriers, and facilitators influence GAT access and desire, and how to improve GAT access in VA and CC.

Risks and Benefits

Anticipated risks and protection against anticipated risks

Database Aim 1

This aim involves retrospective secondary data analyses of existing data. The principal risk to human subjects from these aims is loss of confidentiality, which will be minimized.

We will take several steps to protect participants against potential risks inherent to the proposed research in this aim. The study team has extensive experience conducting secondary data analyses that require strict data security. The Bedford VAMC healthcare systems and VINCI also have well-developed systems and training for preserving data security and confidentiality. These systems will be augmented by the additional security provided by the VINCI system. Data for all participants will be kept strictly confidential by the following means: Source data files will be stored behind the VA firewalls. These data files will be accessed only by data analysts and investigators working on this study. All investigators and project staff will have received IRB and HIPAA training prior to participation in this study. Individual patient identifier information will be removed from study data files as soon as possible after database linkage. In order to avoid any negative consequences of loss of confidentiality, clinicians and other related staff will not be privy to the individual findings, as data will be presented in aggregate in publications and presentations. Unique study-specific identifiers will be assigned to support accurate linkage of data on the same individuals across multiple data files. We will maintain an encrypted secure data dictionary linking the study identifier to the personal identifiers, which will be kept in compliance with the VA Records

Control Schedule after the IRB approval. Analysis files of de-identified data will be created by standard SAS and related analytic programs.

Survey Aim 2

Psychological risks posed by the research are primarily related to the sensitivity of some of the survey measures and interview questions. Items include thoughts, feelings, and personal difficulties that may be private, including questions about history of violence, discrimination, and mental health. These questions may make participants uncomfortable or be perceived as an intrusion on their privacy. Answers to these questions could pose a risk if the information were known and linked to identifiable individuals.

We will take several steps to protect participants against potential risks inherent to the proposed research. Potential psychological risks, including discomfort associated with disclosure of information, feelings of compromised privacy, distress caused by increased awareness of one's own behavior or symptoms, and possible short-term exacerbations of psychological distress, will be addressed in the Information Statement. Participants will be informed of potentially disturbing questions on the Information Statement during the consent process before they agree to participate to minimize the likelihood that participants will experience stress or discomfort. Participants will be encouraged to contact the study office at any time should they have any concerns about their participation or experience any distress. Initial and continuing participation will remain strictly voluntary; participants will remain free to terminate participation at any time without penalty.

Our risk management activities for the survey will also include (based on the VA Sprint Guidelines for Risk Management in Surveys ([Risk Management Resources for Working with VA Research Participants](#)):

1. We will inform patients on the survey cover page that we will not provide individual feedback on survey responses, as their surveys may not be reviewed in real time. We will encourage them to reach out to their clinician, the Veterans Crisis Line, or emergency services if they are experiencing distress or thoughts of suicide.
2. We will provide patients with resources on each survey cover that contains options for self-referral, depending on the participant's self-assessed level of need:
 - **Veterans Crisis Line:** Veterans and their loved ones can call **[name]** and **Press 1**, [chat online](#) at VeteransCrisisLine.net, or send a text message to **[name]** to receive confidential support 24 hours a day, 7 days a week, 365 days a year.
 - **Emergency Services:** As an alternative to calling the Veterans Crisis Line, participants may choose to call 911 in the case of an emergency.

Qualitative Aim 3

Transgender Veterans: There is a risk that transgender Veterans may feel uncomfortable sharing sensitive information with researchers about their experiences with gender affirming treatment and social determinants of health barriers. To minimize this risk, we will perform a rigorous informed consent process that stresses that participation is completely voluntary, and they can choose to skip any interview questions or withdraw from the study at any point. We will also ensure that participants know that they can decline to have their interview audio recorded.

There is also a risk that transgender Veterans may feel coerced to participate due to their use of VA care and the availability of compensation for their time. To minimize these risks, we will compensate participants for their time at a level consistent with other VA research studies. Participants will also receive the full compensation amount even if they choose to withdraw their participation during the interview process. Finally, we will reiterate that participation will in no way impact the care that they receive from the VA.

LGBTQ+ VCCs: As VA employees, there is the potential risk that LGBTQ+ VCCs who may not want to participate in this VA study may feel coerced to do so. We will make it clear that participation is voluntary, not mandatory, and will not impact their VA employment in any way. At any point during the subject's participation, if the participant should want a break or should want to stop participating, they will be informed that they can do so at any time without consequence.

Mishandling of research data would compromise participant confidentiality. All possible measures will be taken to assure participant confidentiality. A secure, password protected database will be constructed to record the names of study participants, with a cross-link to a unique identification number. This will be stored on a secure VA server. Audio-recorded interviews will be transferred immediately to an encrypted VA laptop and erased from the recorder.

Safety Issues. All participants will be provided with study contact information should they have any questions or concerns regarding the study and wish to speak with study staff. We will also ensure that the study office number is monitored during every business day and will return all phone calls within 48 hours. The voice message will instruct callers to hang up and dial 911 in case of an emergency and provide them with the 24-hour VA National Crisis Line, which provides confidential chat support 24 hours a day, 7 days a week. Calls received in the study office will be documented on a tracking log and participants will be provided with resources and referrals as necessary.

Confidentiality.

Database Aim 1: The study team has extensive experience conducting secondary data analyses that require strict data security. The Bedford VAMC healthcare systems and VINCI also have well-developed systems and training for preserving data security and confidentiality. These systems will be augmented by the additional security provided by the VINCI system. Data for all participants will be kept strictly confidential by the following means: Source data files will be stored behind the VA firewalls. These data files will be accessed only by data analysts or programmers and investigators working on this study. All investigators and project staff will have received IRB and HIPAA training prior to participation in this study. Individual identifier information, both patient and clinician, will be removed from study data files as soon as possible after database linkage. In order to avoid any negative consequences of loss of confidentiality, clinicians and other related staff will not be privy to the individual findings, as data will be presented in aggregate in publications and presentations. Unique study-specific identifiers will be assigned to support accurate linkage of data on the same individuals across multiple data files. We will maintain an encrypted secure data dictionary linking the study identifier to the personal identifiers, which will be kept in compliance with the VA Records Control Schedule after the IRB approval. Analysis files of de-identified data will be created by standard SAS and related analytic programs.

Survey Aim 2: All research materials will remain confidential and secure, restricted to researchers on this project who have extensive training in maintenance of privacy and

confidentiality. Upon enrollment in the study, participants will be assigned a random Subject ID number via VA Qualtrics. All data will be indexed by this ID number and stored in accordance with VA privacy and information security policies. All data collected from participants will be indexed by random Subject ID numbers and stored on secure VA Qualtrics and VA research servers, accessible only by approved study personnel. Participants will be informed that only the study team will have access to de-identified data collected in the study. No participants will be identified in any manner in publications. In addition to participants' names and email addresses, we will need to collect mailing addresses for purposes of providing payment. A separate restricted access spreadsheet will contain only this information. Access to the CHOIR building is restricted. All space accessible to the public is separated from research offices. Access to the computer systems is restricted and password protected. All research computers are located in locked rooms and data files are password protected.

Qualitative Aim 3: The research team will take all possible measures to ensure confidentiality during and following interviews. First, participants will be assured that they are free to refrain from answering any questions they do not wish to answer. In previous similar studies, we have found that participants rarely refuse to answer questions when they are collected in a clear and professional manner. Second, during interviews, participant confidentiality will be protected by safeguarding names and identities of participants through the use of unique participant ID numbers, and by ensuring that phone/Microsoft Teams interviews occur at a time and place where both the researcher and participant have privacy. Following interviews, all data (audio recordings, transcripts, and researcher notes) will be coded with a unique ID number for the individual participant. The key code linking participant's name and number will be password protected and stored separately from the data, and only the study team will have access to it. All research data and any documents containing identifiers will be stored on a secure VA server or stored in a locked file cabinet in a locked office. Digital audio recordings will be transcribed using a VA-contracted secure transcription service. Recordings and transcripts will be stored onto the secure VA server as soon as possible and erased from the audio recorders. The Bedford VA servers are backed up regularly.

Results reported in presentations or publications will not contain any individual identifiers. All potential participants will be informed of any risks of participating in this research, so they can make an informed decision regarding participation.

Participant burden. To reduce participant burden, we will minimize survey items to the number necessary and scientifically justified, and by using branching logic where appropriate. Qualitative interviews will proceed at a pace comfortable for the trans Vet and LGBTQ+ VCC participants and will be completed in 45-60 and 30-45 minutes, respectively.

Benefits. There are no direct benefits to participants included in this study. Patients in the VA and in other healthcare systems may benefit from the study findings. Acquiring critical information to identify the needs, preferences, and perceived barriers and facilitators for gender-affirming treatment in this vulnerable and understudied VA population outweigh the risk of breach of confidentiality inherent in the database analyses, national survey and qualitative interviews.

5.2 Recruitment Methods

Database Aim 1

This is a secondary data analysis utilizing exclusively already collected administrative data. Subjects will be identified through VA administrative databases.

Survey Aim 2: Prior to deploying the national survey, we will pilot test the survey with approximately 5-10 transgender and/or gender diverse Veterans. Recruitment for pilot testing of the survey will consist of outreach to local LGBTQ+ Veteran Care Coordinators (VCCs) in VISN 1. We will also announce the study on the VA's LGBTQ+ Health's public-facing website where they post information about LGBTQ+ Veteran research participation opportunities. Should we need additional assistance with recruitment, we will also leverage the TGD Veteran Consultants on our advisory group and TGD veterans recruited for the pilot testing to assist in recruiting additional participating for this testing phase (i.e., snowball sampling recruitment). Last, we will reach out to local Veteran Service Organizations (VSOs) that serve LGBTQ+ Veterans.

Recruitment will consist of providing the VCCs, the VA LGBTQ+ Health Office, and local VSOs with an approved survey advertisement/posting and Information Statement. The advertisement/posting and Information Statement will provide interested Veterans with the contact information for the study's project manager to "opt in" to the pilot testing phase while explaining that the survey is entirely voluntary and that if they choose not to participate or to end the survey prior to completion, there will be no penalties or loss of VA benefits. Veterans interested in participating in the pilot testing of the survey will be emailed an invitation to participate with links to the survey hosted on the Qualtrics platform. Participants in the pilot testing phase will receive a \$25 gift card as an appreciation for their time. Gift cards will be procured via Purchase Order at the lead site. Once study staff receive the gift cards they will activate and then track distribution of the gift cards to participants using the gift card numbers. Once a subject completes participation study staff will mail a gift card directly to the participant, insuring only appropriate study staff have access to PII and all information and data security protections are followed. The funds for the gift cards have been approved in the study budget by VA HSR, which is funding the study.

We anticipate inviting approximately 10,000 trans Vets with a gender dysphoria diagnosis and/or self-reported gender identity as transgender and gender diverse to participate in the national survey and expect up to 1,500 will enroll and complete the survey. Recruitment for the national survey will consist of direct outreach to prospective research participants identified in Aim 1 through a mailed or emailed recruitment letter and Information Statement alerting Veterans about the survey, providing details about the individuals' rights as a research participant and inviting them to participate in the study. The letter will explain that the survey is entirely voluntary and that if they choose not to participate or to end the survey prior to completion, there will be no penalties or loss of VA benefits. The communication will make clear that the survey responses are confidential and that the Veteran's name or any other personally identifying information will not be used in any report of the survey results. The IRB's telephone number will be provided as a means for the potential participant to use to verify that the study constitutes VA research. Additionally, the study project manager's telephone number will be provided for the Veteran to call with questions about the study or if they wish to opt out of the study.

Veterans will be contacted as follows:

Contact	Method	Specifics
---------	--------	-----------

Contact 1	First Letter	All Veterans with a gender dysphoria diagnosis in the past 2 years and/or self-identified gender identity as transgender and gender diverse will be sent a recruitment letter via mail and/or email inviting them to participate in the study and offering the ability to opt-out, complete the survey online (either through mobile device, tablet or desktop), call in to the study project manager's number to complete the survey with the study manager or request that a paper survey is mailed to them.
Contact 2	Second letter	A second letter will be sent via mail and/or email approximately 10 days after the first letter.
Contact 3	Reminder Postcard	Approximately ten to twelve days after the second letter, we will send a reminder postcard and/or letter and/or email reinforcing basic information provided earlier and directing people to the website or to call the study project manager's number to complete the survey.
Contact 4	Telephone	Seven days after the reminder postcard is sent, study team staff will begin to make telephone calls to non-responders. Up to 3 attempts will be made, with one message left.

For individuals who are interested in participating, two automated email reminders will be sent by Qualtrics to the interested Veteran to remind them to complete the survey. For those trans Vets who do not have an email address or who prefer paper-and-pencil measures, the study project manager will mail forms along with postage-paid envelopes. Our operational partner, LGBTQ+ Health, will also help disseminate IRB approved recruitment letters to their internal and external distribution email groups to assist with recruitment of trans Vets.

Should our enrollment be lower than originally anticipated using VA Corporate Data Warehouse, we will also deploy additional recruitment methods that align with our recruitment methods used in pilot testing. These alternative recruitment methods will include posting an approved advertisement on the VA LGBTQ+ Health Office with the study information, reaching out to LGBTQ+ Veteran Care Coordinators to advertise our study and TGD Veteran Consultants on our advisory group and TGD veterans recruited for the pilot testing to assist in recruiting additional participating for this testing phase (i.e., snowball sampling recruitment). Last, we will reach out to local Veteran Service Organizations (VSOs) that serve LGBTQ+ Veterans. Recruitment will consist of providing the local VSOs with an approved survey advertisement/posting and Information Statement. In both of these recruitment methods, the interested veterans will "opt-in" to the study by contacting the study team directly. The study team will not call veterans recruited with this technique without the veteran first making contact..

Participants who complete the full survey will receive a \$30 gift card. Gift cards will be procured via Purchase Order at the lead site. Once study staff receive the gift cards they will activate and then track distribution of the gift cards to participants using the gift card numbers. Once a subject completes participation (i.e., answers all questions on the survey) study staff will mail a gift card directly to the that participant, insuring only appropriate study staff have access to PII

and all information and data security protections are followed. The funds for the gift cards have been approved in the study budget by VA HSR&D, which is funding the study. If the participant does not complete the survey, we will use the information/incomplete data the participant already provided in the survey, unless they notify us that they do not want their information to be used.

Qualitative Aim 3:

Transgender Veterans: We anticipate interviewing ~ 70 trans Vets. We will seek diversity in the sample based on race, gender identity, VA region to ensure geographic representation and care received in VA vs. CC.

We will recruit qualitative interview participants from survey respondents. We will ask survey respondents in the survey if they would be willing to participate in a follow-up telephone interview. The following survey question will be reviewed for interest: "Our research team plans to interview trans Vets to learn more about their experiences accessing gender-affirming treatment in VA and VA Community Care. Would you be interested in participating?"

VA staff will mail or email potential participants a letter and an Information Statement alerting them about the interview opportunity, providing details about the individuals' right as a research participant. The letter will explain that the survey is entirely voluntary and that if they choose not to participate or to end the interview prior to completion, there will be no penalties or loss of VA benefits. The letter will make clear that the interview responses provided are confidential and that the Veteran's name will not be used in any report of the results. The IRB's telephone number will be provided as a means for the potential participant to use to verify that the study constitutes VA research. Additionally, the telephone number of the study project coordinator will be provided for the Veteran to call with questions about the study or if they wish to opt out of the study.

Two weeks after the initial letter is mailed or emailed, VA research staff will begin follow-up via phone. The purpose of the phone call is to further explain the research and requirements and assess their interest in participating. Veterans will be informed that participation is fully voluntary and that their decision regarding participation will in no way affect their access to services or the quality of care they receive at the VA. Up to two additional letters and/or emails and two additional calls may be made if there is no response.

Should we experience challenges recruiting the survey respondents for the qualitative interviews, we will reach out to LGBTQ+ Veteran Care Coordinators (LGBTQ+ VCCs) to disseminate the IRB-approved recruitment letter for the interviews. The LGBTQ+ VCCs will provide the letter to all transgender Veterans at their specific sites. We will also reach out to Veteran Service Organizations (VSOs) that serve LGBTQ+ Vets, (e.g., Modern Military), to introduce the study for recruitment of trans Vets enrolled in VA care. Further, we will also post an approved advertisement on the VA LGBTQ+ Health Office for recruitment for the qualitative aim. Should we need additional assistance with recruitment, we will also leverage the TGD Veteran Consultants on our advisory group and TGD veterans recruited for the pilot testing to assist in recruiting additional participating for this testing phase (i.e., snowball sampling recruitment).

Participants will be compensated with a \$25 gift card. Gift cards will be procured via Purchase Order at the lead site. Once study staff receive the gift cards they will activate and then track distribution of the gift cards to participants using the gift card numbers. Once a subject completes participation study staff will mail a gift card directly to the that participant, insuring

only appropriate study staff have access to PII and all information and data security protections are followed. The funds for the gift cards have been approved in the study budget by VA HSR&D, which is funding the study.

LGBTQ+ VCCs: We will recruit ~ 20 LGBTQ+ VCCs nationally through two approaches. First, we will recruit them through their regularly scheduled monthly calls. The VA LGBTQ+ Health Program Office will facilitate the study team's joining this call where we will announce recruitment for our study. Second, the study team potentially with the help of the VA LGBTQ+ Health Program Office will send IRB approved recruitment email and Information Statement to LGBTQ+ VCCs at all sites in which we will invite them to participate in our study. We will be limited to no more than 3 email messages to LGBTQ+ VCCs. We will use an opt-in approach, namely that we will not contact anyone by phone unless they email us back and express a willingness to participate.

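### The national survey's $30 payment depends on answering every question, which sits badly with the interview payment rule and with the plan's own allowance for skipped items

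*Combined protocol and SAP*

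**What the plan says.** Section 5.2 (Recruitment Methods, Survey Aim 2) introduces the payment with "Participants who complete the full survey will receive a" $30 gift card. It then defines what completing means: "Once a subject completes participation (i.e., answers all questions on the survey) study staff will mail a gift card". No partial payment is described. Nor does the protocol describe a right to skip survey items or a declined-answer option.

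Four other places bear on this rule:

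- **No penalty for stopping.** The survey risk text in Section 5.1 says "participants will remain free to terminate participation at any time without penalty". The recruitment letter described in Section 5.2 will say that "if they choose not to participate or to end the survey prior to completion, there will be no penalties or loss of VA benefits".
- **Sensitive content.** Section 5.1 says of the survey and interview questions: "Items include thoughts, feelings, and personal difficulties that may be private, including questions about history of violence, discrimination, and mental health".
- **Use of incomplete surveys.** Section 5.2 says: "If the participant does not complete the survey, we will use the information/incomplete data the participant already provided in the survey", unless the participant objects.
- **Interviews (Aim 3).** Section 5.1 names compensation as a possible source of coercion. In answer it lets interviewees skip any question and adds: "Participants will also receive the full compensation amount even if they choose to withdraw their participation during the interview process".

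Section 5.6 (Missing data) expects some items to go unanswered. It plans a complete-case primary analysis and, for items with at least 10% missing, a look at patterns of missingness and an imputation sensitivity analysis.

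**The concern.** Two things are at stake.

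The first is voluntariness. Someone who works through the whole survey but declines one question on violence or mental health gets nothing under the written rule, while the answers they did give are analysed. The protocol already treats payment as a possible pressure on this population and guards against it in the interviews. It does not do so in the survey.

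The second is measurement. A skipped item is visible, and the analysis plan has tools for it. An answer entered only to secure the gift card looks like any other answer. Barriers are the independent variables in the primary models of Section 5.6, and Section 2.0 names violence and discrimination among them. A payment rule that discourages honest skips on those items could therefore replace a problem the plan can see with one it cannot.

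**Working it through.** The plan states no figure on this point, so the main check sets the passages side by side.

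**1. Who is paid, by scenario, as written**

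| Scenario | Paid? | Data used? |
|---|---|---|
| National survey, every question answered | Yes, $30 (5.2) | Yes |
| National survey, end reached, one item skipped | No (5.2) | Yes (5.2) |
| National survey, stopped part-way | No (5.2) | Yes, unless the participant objects (5.2) |
| Interview, one question skipped | No such condition (5.1, 5.2) | Yes |
| Interview, withdrawn part-way | Yes, in full (5.1) | Yes, unless withdrawal of data is requested in writing (5.7) |

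The second and third rows differ from the fourth and fifth although the population is the same and the topics overlap. The payment sentences for the pilot survey and for the interviews speak only of completing participation. The all-questions definition appears for the national survey alone, so the pilot, as described, will not test it.

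**2. What the missing-data plan can see**

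- A skip counts towards the 10% threshold, can be studied for predictors of missingness, and can be imputed in the sensitivity analysis.
- An answer given only to qualify for payment counts as observed. It enters the complete-case primary analysis and triggers none of these steps.

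**3. How strict an all-questions rule could be (illustration only)**

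Let k be the number of items shown to a respondent and q the chance of skipping each one, with skips independent. The share answering every item is (1 − q)^k. Neither k nor q is in the documents; both are assumed here.

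| q | k = 50 | k = 100 | k = 150 |
|---|---|---|---|
| 0.2% | 90.5% | 81.9% | 74.1% |
| 0.5% | 77.8% | 60.6% | 47.1% |
| 1% | 60.5% | 36.6% | 22.1% |
| 2% | 36.4% | 13.3% | 4.8% |

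For shorter surveys, the share skipping at least one item is 1 − (1 − q)^k:

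- k = 20, q = 0.5%: 9.5%
- k = 40, q = 1%: 33.1%
- k = 60, q = 2%: 70.2%

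The range is too wide to serve as an estimate. It shows only that a low skip rate per item can still disqualify a sizeable share when the test is every item.

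**4. Cost of paying all submitters**

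Section 5.2 expects about 10,000 invitations and up to 1,500 completed surveys (1,500 / 10,000 = 15%). At $30 each, 1,500 × $30 = $45,000.

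**The case against.** The case for leaving the rule alone has several parts.

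- **No promise is broken.** A reader might infer that the payment rule contradicts the no-penalty assurances. The documents do not support that. Sections 5.1 and 5.2 promise no penalty and no loss of VA benefits for stopping; neither promises payment. Failing to earn a completion incentive is not plainly a penalty, and finishing with one item skipped is not the case those assurances address. This stands: it is a tension only.
- **Branching.** A reader might infer that the rule cannot be applied, because branching logic routes people past some items. The natural reading is all questions shown to that respondent. This also stands.
- **Unseen instrument.** The survey itself and the text of the Information Statement are not in the documents. If a declined answer is offered and counts as an answer, most of the pressure disappears. This stands as a limit on how much can be claimed. It does not remove the need to say what counts as complete, particularly as Section 5.2 allows paper forms, on which blanks can occur.
- **Interviews are a different mode.** True, but the coercion risk that Section 5.1 names comes from payment and use of VA care, and both apply equally to survey respondents.
- **Completeness protects data quality.** Payment with no condition would reward blank submissions, which matters if the back-up recruitment by advertisement and snowball sampling is used. This stands, and the fix has to include a screen.

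**Conclusion.** The point holds as an inconsistency that is cheap to repair. The survey rule withholds payment for a single skipped item, while the same protocol uses that person's data, plans for skipped items in its analysis, and protects interviewees from the same pressure. The no-penalty assurances are strained but not broken.

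The effect on data quality is a possibility of unknown size. A reader might infer that respondents will give filler answers, and that the error will vary with the exposures because financially strained Veterans feel the pressure most. The documents establish neither. The 31% unemployment and 28% housing instability in Section 2.0 come from a cited earlier study, not from this survey's sample, and nothing in the plan gives a direction or size of bias. What can be said is narrower: if such answers occur, the 10% missingness check and the imputation analysis would not pick them up.

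The illustrative percentages should not be quoted as a forecast of unpaid or invalid responses. They rest on assumed item counts and skip rates and on independent skips. If skips cluster within people, the formula overstates the share who skip at least one item.

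**What to change.** In Section 5.2, replace the parenthetical definition of completion with wording such as: *reaches the end of the survey and submits it; an item shown to the respondent that is skipped or marked as prefer not to answer does not forfeit payment*. Add a simple check that excludes blank or duplicate submissions from payment.

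Three changes go with it:

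- Offer a prefer-not-to-answer option on the sensitive items, if the instrument does not already have one.
- State the payment rule in the Information Statement, which Section 5.3 says already covers compensation.
- Decide what happens to payment when a survey is abandoned, and make the survey risk text and interview compensation text in Section 5.1 and the recruitment-letter and incomplete-data text in Section 5.2 agree with that decision.

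The cost is a wording change, slightly more visible item non-response, some additional gift cards and the screening step. Payment to submitters stays within $45,000 if they number no more than the planned 1,500. Paying for abandoned surveys as well could exceed that sum, so that decision needs its own budget check. No change to the sample size or the planned models is needed.
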